ABC = activated B-cell; ADA = anti-drug antibodies; AE = adverse event; BMI = body-mass index; BP = blood pressure; C = cycle; CAR-T = chimeric antigen receptor T-cell therapy; CLS = capillary leak syndrome; CK = creatine phosphokinase; CRS = cytokine release syndrome; CT = computerized tomography; D = day; ECG = electrocardiogram; ECHO = echocardiogram; ECOG = Eastern Cooperative Oncology Group; eCrCl = estimated creatinine clearance; eCRF = electronic case report form; EOI = end of infusion; EoT = end of treatment; EQ-5D = EuroQol Group Quality of Life – 5-dimensions; GCB = germinal center B cell; HbA1c = glycated hemoglobin; HBV = hepatitis B virus; HCV = hepatitis C virus; HIV = human immunodeficiency syndrome; LTFU = long-term follow-up; NHL = non-Hodgkin's lymphoma; HR = heart rate; IRR = infusion-related reaction; LVEF = left ventricular ejection fraction; MRI = magnetic resonance imaging; MUGA = multigated acquisition; NAb = neutralizing antibody; NYHA = New York Heart Association; OTC = over-the-counter; PD = progressive disease; PK = pharmacokinetic; RNA = ribonucleic acid; RR = respiratory rate; SCR = screening; SCT = stem cell transplant; SD = stable disease; STFU = short-term follow-up; TIW = three times a week.

- a The screening period is up to 35 days prior to enrollment. All local/central laboratory safety assessments and radiological assessments must be collected within 28 days prior to enrollment.
- b All assessments are performed any time before dosing unless otherwise indicated. Predose assessments may be performed up to 1 day prior to dosing (except for cytokines/immunoglobulins/complement/histamine which should be collected just prior to dosing).
- c The Day 15 visit is applicable for subjects receiving the weekly dosing schedule.
- d Upon discontinuation of treatment, as soon as possible (up to 14 days) after the last dose, and before the start of new therapy.
- e A STFU visit occurs 30 days ( $\pm$  3 days) after the last dose. The STFU visit can be done via a clinic visit (recommended) or via a telephone call (if subject cannot attend a clinic visit or has started a new anticancer treatment or a new NHL treatment). If performed via a telephone call, only AEs and concomitant medications will be collected.

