## 5.1 Inclusion Criteria

Subjects meeting ALL of the following inclusion criteria will be eligible for participation of the study:

1. Subjects must be informed about the study and fully consent to participation as demonstrated by signing the written ICF before any screening procedure.
2. Male and female subjects  $\geq 18$  years of age at the time of informed consent
3. Subjects must have relapsed or refractory DLBCL according to the Revised European American Lymphoma/World Health Organization classification ([Swerdlow, 2016](#)). Subjects must have proof of CD20+ DLBCL, based on either:
  - a. historical biopsies (obtained with diagnosis of relapsed or refractory disease), or
  - b. fresh biopsies
  - c. bone marrow biopsy, excisional lymph node biopsy, and core biopsy of any involved organ are all acceptable methods; Fine Needle Aspirate is not acceptable.

NOTE: Composite lymphoma (DLBCL and indolent histology in the same specimen) is also acceptable.
4. Subjects must have received at least 2 SoC regimens (including anti-CD20 antibody therapy) appropriate for DLBCL treatment.
  - a. Subjects whose prior therapy includes CAR-T-cell therapy are eligible
  - b. Subjects who underwent stem cell transplant (SCT)  $> 100$  days for autologous SCT or  $> 180$  days for allogeneic SCT before study drug administration.
  - c. Subjects who have been ineligible for SoC DLBCL treatment(s) may be eligible at the investigator's discretion, upon sponsor approval.
5. Subjects must have at least 1 bi-dimensional tumor lesion at screening that is measurable by CT and/or magnetic resonance imaging (MRI) according to the Lugano criteria ([Cheson, 2014](#)). Bi-dimensionally measurable tumor lesion by CT and/or MRI is defined as longest diameter of  $> 1.5$  cm for lymph nodes and  $> 1.0$  cm for extranodal disease.
6. Subjects must have life expectancy of  $> 3$  months from the start of treatment.
7. Subjects must have ECOG performance status of 0-2.
8. Subjects must have met ALL the following laboratory criteria:
  - a. absolute neutrophil count (ANC)  $\geq 1.0 \times 10^9/L$  with no myeloid growth factors (granulocyte colony-stimulating factor [G-CSF] or granulocyte-macrophage colony-stimulating factor preparations) administered within 2 weeks of C1D1
  - b. platelet count  $\geq 50 \times 10^9/L$  with no Thrombopoietin-receptor agonists agents or platelet transfusions given within 2 weeks of C1D1

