- c. hemoglobin  $\geq 8.0$  g/dL with no erythropoietin stimulating agents or peripheral red blood cell (PRBC) transfusions within 2 weeks of C1D1
- d. creatinine clearance (CLcr) to be  $\geq 50$  ml/min either measured or estimated using the Cockcroft-Gault formula ([Section 10.2.2.2](#)).
- e. total bilirubin (or direct bilirubin for patients with Gilbert's disease)  $< 1.5 \times$  upper limit of normal (ULN)
- f. alanine transaminase (ALT)  $\leq 3.0 \times$  ULN (or  $\leq 5.0 \times$  ULN if liver involvement).
- g. aspartate aminotransferase (AST)  $\leq 3.0 \times$  ULN (or  $\leq 5.0 \times$  ULN if liver involvement).
- h. international normalized ratio (INR) or prothrombin time (PT)  $\leq 1.5 \times$  ULN (unless on therapeutic anticoagulants)
- i. Activated partial thromboplastin time  $\leq 1.5 \times$  ULN (unless on therapeutic anticoagulants)

9. Have adequate serum albumin, as determined by:

- a. albumin  $\geq 3.0$  g/dL

10. QT interval correction for heart rate using Fridericia's formula (QTcF)  $\leq 480$  ms determined as the average of 3 QTcF values from the triplicate ECG obtained at screening.

11. Women of reproductive potential must have a negative highly sensitive pregnancy test within 72 hours before the start of treatment. Women who are postmenopausal or permanently sterilized (eg, tubal occlusion, hysterectomy, bilateral salpingectomy) may be considered as not of reproductive potential.

12. Subjects of reproductive potential must agree either to abstain continuously from heterosexual intercourse or to use a highly effective birth control method from signing the informed consent until the STFU visit for females and until 90 days after the last dose of MT-3724 for males. Refer to [Section 10.4](#) for guidance on contraception.

13. Subject must be able to comply with all study-related procedures and medication use.

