### Prior or Current Therapies

1. Received any amount of anti-CD20 mAbs within the following periods before the start of treatment:
  - a. Rituximab (Rituxan®/MabThera® or rituximab biosimilar): within 84 days (12 weeks); if a subject has received rituximab within 37 weeks before the start of treatment, then serum rituximab level must be negative ( $< 500$  ng/mL) at screening.
  - b. Obinutuzumab (Gazyva®/Gazyvaro®): 184 days
  - c. Ofatumumab (Arzerra®): 88 days
  - d. Any other anti-CD20 agents (eg, investigational agents), the washout period is 5 half-lives. The investigator must contact the medical monitor to discuss the most

appropriate washout for non-approved CD20-targeting agents, where the half-life ( $t_{1/2}$ ) is not known.

2. Received approved or investigational treatment for DLBCL (except anti-CD20 agents where exclusion criterion 1 applies and radioimmunoconjugates) within 4 weeks before the start of treatment. For small molecules (MW < 0.9 kDa), the washout is 5 half-lives or at least 2 weeks. Radioimmunoconjugates are excluded within 12 weeks before the start of treatment.
3. Received radiation therapy to tumor lesions that would serve as target lesions (measurable disease) within 4 weeks before the start of treatment, unless the lesion exhibited objective progression between radiation therapy and screening according to the Lugano Classification ([Cheson, 2014](#)).
  - a. Palliative radiation therapy to non-target lesions may be permitted at the investigator's discretion after consultation with the medical monitor and sponsor. See [Section 6.5](#) for more information on permissible use of palliative radiotherapy.
4. Require the use of systemic immune modulators during study treatment:
  - a. Systemic immune modulators include, but are not limited to, systemic corticosteroids at doses > 20 mg/day of prednisone equivalent, cyclosporine and tacrolimus. Please see [Section 6.1.3](#) for more details and exceptions.
  - b. The use of non-steroidal anti-inflammatory drugs (NSAIDS) is permitted.
5. Received any live vaccines within 4 weeks before the start of treatment.
6. Prior treatment with MT-3724.

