14. History or current evidence of neoplastic disease that is histologically distinct from NHL, except cervical carcinoma in situ, superficial noninvasive bladder tumors, curatively treated Stage I-II non-melanoma skin cancer. Subjects with prior, curatively treated cancer > 2 years ago before the start of treatment can be enrolled.

15. Current evidence of new or growing brain or spinal metastases during screening. Subjects with known brain or spinal metastases may be eligible if they:

- a. Had radiotherapy or another appropriate therapy for the brain or spinal metastases; concurrent prophylactic treatment is allowed
- b. Neurologic symptoms must be stable and no worse than Grade 2
- c. Have evidence of stable brain or spinal disease on CT or MRI scan obtained within 4 weeks before signing the informed consent and compared with prior imaging results
- d. Do not require steroid therapy (or, if applicable, have been stable on dose of no more than prednisone 20 mg/day or equivalent by C1D1)

16. Women who are pregnant or breastfeeding.

17. History of non-adherence to the schedule of procedures or medication use.

18. Current evidence of Graft vs Host Disease

19. History or current evidence of significant cardiovascular disease including, but not limited to, the following conditions:

- a. Unstable angina (symptoms of angina at rest) or new-onset angina within 3 months before the start of treatment.
- b. Arterial thrombosis or pulmonary embolism within 3 months before the start of treatment.
- c. Myocardial infarction or stroke within 3 months before the start of treatment.
- d. Pericarditis (any CTCAE grade), pericardial effusion (CTCAE Grade  $\geq 2$ ), non-malignant pleural effusion (CTCAE Grade  $\geq 2$ ) or malignant pleural effusion (CTCAE Grade  $\geq 3$ ) within 3 months before the start of treatment with MT-3724.

- e. Congestive heart failure (New York Heart Association [NYHA] Class III or IV) at screening or left ventricular ejection fraction (LVEF)  $\leq 45\%$ , assessed by echocardiogram (ECHO) or multigated acquisition (MUGA) scan within 1 month before starting study treatment (inclusion of subjects with LVEF between 40% to 45% should be discussed with the medical monitor and approved by the sponsor). (ECHO or MUGA performed within 6 months before screening and at least 28 days after the last cancer therapy is acceptable provided the subject has not received any potentially cardiotoxic agents since then).

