**Table 6-4. MT-3724 Dose Modification Guidance and Specific Management of Toxicities**

	Specific Management	MT-3724 Dose Modificationa

Grade <math>\geq</math> 2 CLS: As defined in CTCAE v5.0, or if at least 2 of the following within the same cycle (unless unequivocally related to underlying condition) reaches the level of Grade 2:
 
 
• Hypoalbuminemia
 
• Hypotension
 
• Edema (peripheral or central, all types) and/or weight gain
 
	
Subjects should be closely monitored for signs of CLS. This includes:
 
 
• Monitoring of vital signs (temperature, heart rate, BP, respiration rate), body weight, edema of any type including both peripheral edema and central edema (such as pleural effusion or signs of dyspnea).
 
• Monitoring of laboratory parameters including hemoconcentration (eg, hematocrit, Hb), and especially albumin and CK in case of clinical symptoms indicative of CLS.
 
 
Investigators should consider supportive measures while on trial regardless of dosing or timing of dosing. If a subject experiences Grade 2 hypotension, orthostasis, edema, or hypoalbuminemia, normal saline and/or an albumin infusion may be given, as needed.
	
Treatment modification due to CLS:
 
 
• For Grade <math>\geq</math> 3 CLS, the MT-3724 treatment must be permanently discontinued.
 
• For Grade 2 CLS, the MT-3724 treatment must be held, and may only be restarted after: 
 
◦ a minimum of 7 days has elapsed after onset of CLS, and
 
◦ all signs and symptoms of CLS have resolved to at least grade 1, and
 
◦ albumin has remained <math>\geq</math> 3.0 g/dL for at least 5 days post last albumin infusion (if required) without additional albumin substitution
 
 
 
 
Subsequent doses of MT-3724 must be:
 
 
• reduced by at least 25%, and
 
• administered once weekly
 
 
or subject may be permanently discontinued at the investigator's discretion.

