#### **10.2.2.4 Rituximab Concentration**

Serum rituximab (RTX) concentration must be assessed at screening if a subject received RTX within 37 weeks before the start of treatment on C1D1. Subjects will be eligible only if the serum RTX concentration is below 500 ng/mL. Serum RTX does not need to be re-evaluated once determined to be "negative", in cases of rescreening.

The serology for RTX concentration should not be assessed in subjects who have received RTX within 84 days before the start of treatment (automatically ineligible based on this criterion). When 37 weeks have elapsed since the last treatment with RTX, [REDACTED]

[REDACTED] The serology for RTX concentration should not be assessed for subjects who never received RTX.

It is recommended to assess RTX serum concentration prior to performing other screening procedures.

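### Criteria 8a-c count the two support-free weeks back from C1D1 and not from the qualifying sample, so a supported blood count can meet them; three related entry checks need reconciling

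*Protocol*

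**What the plan says.** **Blood counts.** Section 5.1 qualifies each count by a support-free period that ends at C1D1:

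- 8a, neutrophils: "granulocyte-macrophage colony-stimulating factor preparations) administered within 2 weeks of C1D1"
- 8b, platelets: "with no Thrombopoietin-receptor agonists agents or platelet transfusions given within 2 weeks of C1D1"
- 8c, hemoglobin: "with no erythropoietin stimulating agents or peripheral red blood cell (PRBC) transfusions within 2 weeks of C1D1"

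The age of the sample is set elsewhere. Table 1-1 footnote a says "All local/central laboratory safety assessments and radiological assessments must be collected within 28 days prior to enrollment", and Sections 8.1.1 and 10.2.1 give the same 28 days, counted from the start of treatment.

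**Albumin.** Criterion 9 asks for at least 3.0 g/dL and adds no condition on albumin infusion. Table 6-4 uses the same 3.0 g/dL for restart after Grade 2 CLS, where the value must hold "for at least 5 days post last albumin infusion (if required) without additional albumin substitution". The DLT list in Section 10.3.9 counts Grade 2 or higher CLS with an albumin fall of at least 0.5 g/dL from the C1D1 value.

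**CNS scan.** Exclusion 15c (Section 5.2) makes subjects with known CNS disease eligible if they "Have evidence of stable brain or spinal disease on CT or MRI scan obtained within 4 weeks before signing the informed consent". Table 1-1 footnote a, the note opening Section 5, and Section 8.1.1 limit radiology to 28 days before enrollment or treatment.

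**Rituximab.** Section 10.2.2.4 says "Serum RTX does not need to be re-evaluated once determined to be" negative, in cases of rescreening. Exclusion 1a says "if a subject has received rituximab within 37 weeks before the start of treatment, then serum rituximab level must be negative".

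**The concern.** A support-free clause exists so that the count reflects the subject's own marrow. It can do that only if the interval runs up to the sample. Here the interval and the sample are dated independently, so a count raised by a recent transfusion or growth factor can satisfy the criterion.

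The consequence would fall mainly on Part 3. Each cohort has 6 subjects. Two DLTs stop the study in Cohort 1; in Cohort 2 they send Part 4 to the Cohort 1 regimen (Section 6.1.1.2). Grade 4 thrombocytopenia and Grade 4 anemia are potential DLTs (Section 10.3.9). An event that the subject's clinical state could also have produced can be classed as possibly related, which counts as related for DLT assignment (Section 10.3.5). The elevated-baseline note in Section 10.3.9 covers AST, ALT and bilirubin but not cytopenias. A subject whose marrow was below the entry floor could therefore contribute a disease-driven event to a very small denominator.

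The other three items are places where sites could apply different entry rules because two passages do not agree.

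**Working it through.** The plan states no figure on this point to reproduce. The check is calendar arithmetic on its own windows, in days before C1D1. I treat enrollment and C1D1 as the same date, since the protocol anchors the 28-day limit to both.

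**1. Counts (8a-c)**

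Inputs: sample at *s* days before C1D1, with *s* from 1 to 28; last support at *t* days before C1D1, with *t* at least *s*; support is permitted if *t* > 14.

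- Support on the same day as the sample (*t* = *s*) is permitted when *s* > 14, that is *s* = 15 to 28: 28 − 14 = 14 of the 28 allowed sample days.
- Support on the day before the sample (*t* = *s* + 1) is permitted when *s* is 14 to 28: 15 of the 28 days.
- Example: platelet transfusion on Day -27, sample on Day -26. The transfusion is 27 days before C1D1, outside the 14-day bar, so 8b is met by a value measured one day after transfusion.
- For later samples the latest permitted support is at *t* = 15, so the protected gap before the sample is 15 − *s* days. At *s* = 7 that is 8 days; only at *s* = 1 is it the full 14.

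If the 14 days were also counted back from the sample, the look-back for the oldest allowed sample would reach 28 + 14 = 42 days before C1D1.

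**2. Later checks, set beside the entry threshold**

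| Later check | Where | Entry floor re-applied? |
|---|---|---|
| Hematology on Day 1, with a local sample if central results will not be ready before dosing | Table 1-1; Section 10.2.1 | No |
| Medical monitor review of screening data | Section 5 | Not to a new value |
| Investigator's health check before the first dose | Section 5 | No, general judgement |

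**3. CNS scan (15c)**

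Read alone, with consent on the first day of a 35-day screening period: 28 + 35 = 63 days, or 9 weeks, against 28 days in the general rule (63 / 28 = 2.25). Read literally, a scan taken after consent does not satisfy 15c at all.

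**4. Rituximab (10.2.2.4 against 1a)**

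37 weeks × 7 = 259 days. Exclusion 1a bars rituximab within 84 days, so the level test matters from day 85 to day 259: 259 − 84 = 175 days. The two passages collide only for a rescreened subject who received rituximab after the earlier negative result and falls in that band.

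**The case against.** The best reply on counts is that a supported value is unlikely to pass unnoticed. A Day 1 count should normally be available before dosing and lies inside the support-free fortnight. Section 9.3.1.1 takes baseline as the most recent pre-treatment value, not the older screening sample. Every DLT also needs the sponsor to judge it at least possibly related, after consulting investigators. All of this stands and lowers the risk. It does not close the gap, because no passage requires the Day 1 value to meet 8a-c.

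Stronger readings are tempting on the other items, and the documents do not support them:

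- **A 9-week-old CNS scan is allowed.** A reader might infer this from 15c. But the note in Section 5 accepts pre-consent radiology only within 28 days of planned Day 1, two other places repeat that limit, and exclusion 15 bars new or growing CNS lesions during screening. This is a contradiction, not a permission.
- **Outdated rituximab results can admit subjects.** Without further rituximab, age does not make a negative result false. With it, exclusion 1a and the opening of Section 10.2.2.4 itself still call for a test. Text in the next paragraph of that section is redacted and cannot be judged.
- **Entry is wrongly looser than restart for albumin.** Table 6-4 concerns subjects who have just had Grade 2 CLS on drug, and its infusion clause applies only where an infusion was needed. Albumin is also reviewed before every Cycle 1 dose (Table 1-1), although that row gives no threshold. Low albumin already present at C1D1 does not by itself meet the CLS DLT, which needs a fall from that value. An infusion just before C1D1 would, however, raise the value from which the fall is measured.
- **C1D1 is the wrong anchor.** The documents show anchors that do not match; they do not establish which is right.

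**Conclusion.** The gap in criteria 8a-c is real on the text. For half of the permitted sample days (14 of 28), support given on the day of the sample is compatible with the criterion, and no later check restores the threshold. This rests on reading the two-week bar as 14 days before C1D1 and the sample limit as 28 days, as written.

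The albumin, CNS-scan and rituximab items are narrower: one mismatch of conditions and two conflicts between passages.

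The effect on DLT counts is possible but cannot be sized. The documents give no rate of supported counts, CNS disease or rescreening, and the number of subjects affected is probably small. That one event would be half of the two-DLT limit restates the rule and is not evidence that misattribution will occur. No effect on alpha, power or the Part 4 decision rule is claimed.

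**What to change.** **Criteria 8a-c.** Require the two-week support-free interval before the qualifying sample as well as before C1D1. The cost is one wording change and, for a recently supported subject, an occasional repeat sample or a short delay.

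**Reconcile, in the same amendment:**

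- *Criterion 9, Table 6-4 and Section 10.3.9.* State whether the entry albumin and the C1D1 reference value may be infusion-supported, and explain any intended difference from the restart condition. The choice is a clinical one for the sponsor.
- *Exclusion 15c and the 28-day radiology rule.* Make the passages agree on the date from which the CNS scan is counted, and say whether a scan taken during screening counts.
- *Section 10.2.2.4 and exclusion 1a.* Limit the retest waiver to subjects who have had no rituximab since the negative result. This adds a test only for the rare re-exposed subject.

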## 5.2 Exclusion Criteria

Subjects who meet ANY of the following criteria must be excluded:

### Prior or Current Therapies

1. Received any amount of anti-CD20 mAbs within the following periods before the start of treatment:
  - a. Rituximab (Rituxan®/MabThera® or rituximab biosimilar): within 84 days (12 weeks); if a subject has received rituximab within 37 weeks before the start of treatment, then serum rituximab level must be negative ( $< 500$  ng/mL) at screening.
  - b. Obinutuzumab (Gazyva®/Gazyvaro®): 184 days
  - c. Ofatumumab (Arzerra®): 88 days
  - d. Any other anti-CD20 agents (eg, investigational agents), the washout period is 5 half-lives. The investigator must contact the medical monitor to discuss the most

appropriate washout for non-approved CD20-targeting agents, where the half-life ( $t_{1/2}$ ) is not known.

2. Received approved or investigational treatment for DLBCL (except anti-CD20 agents where exclusion criterion 1 applies and radioimmunoconjugates) within 4 weeks before the start of treatment. For small molecules (MW < 0.9 kDa), the washout is 5 half-lives or at least 2 weeks. Radioimmunoconjugates are excluded within 12 weeks before the start of treatment.
3. Received radiation therapy to tumor lesions that would serve as target lesions (measurable disease) within 4 weeks before the start of treatment, unless the lesion exhibited objective progression between radiation therapy and screening according to the Lugano Classification ([Cheson, 2014](#)).
  - a. Palliative radiation therapy to non-target lesions may be permitted at the investigator's discretion after consultation with the medical monitor and sponsor. See [Section 6.5](#) for more information on permissible use of palliative radiotherapy.
4. Require the use of systemic immune modulators during study treatment:
  - a. Systemic immune modulators include, but are not limited to, systemic corticosteroids at doses > 20 mg/day of prednisone equivalent, cyclosporine and tacrolimus. Please see [Section 6.1.3](#) for more details and exceptions.
  - b. The use of non-steroidal anti-inflammatory drugs (NSAIDS) is permitted.
5. Received any live vaccines within 4 weeks before the start of treatment.
6. Prior treatment with MT-3724.

